9.3.6. Endpoints of Interest

To assess tofacitinib utilization patterns, the main endpoint of interest to be captured in the interim and final study reports will be the indication for tofacitinib use, classified as on-label, off-label, or unknown, based on medical events (diagnoses and/or medication use) identifiable around the time of the first ever tofacitinib prescription. The date of first prescription of tofacitinib during the study period is the index date as described in Section 9.3.4.1. All patients' tofacitinib use will be classified as on-label indication, off-label indication or unknown indication according to the first prescription of tofacitinib received, regardless of later prescriptions. The on-label, off-label and unknown indication classifications will be made based on the authorized indication(s) as of the index date.

For the active surveillance portion of the study, the safety events of interest (to be defined via ICD-code based algorithms in the SAP) which will also be captured in the interim and final study reports include the following:

- Malignancy, excluding NMSC
- Lung cancer
- Lymphoma
- NMSC
 - Serious infections
 - Opportunistic infections (e.g. tuberculosis)
 - HZ reactivation

- MACE
- VTE (DVT and PE)
- Myocardial Infarction (MI)
- Hepatic events
- PML (PML)
- GI perforations
- ILD
- Fractures
- Surgery for UC (e.g. colectomies, partial colectomies, and proctocolectomies; full list of procedures to be detailed in SAP)
- Death

Of note, due to limitations related to the Marketscan database, only in-hospital deaths can be captured (outcome will be defined via an algorithm currently under development, details of which will be outlined in the SAP). Deaths occurring in other environments such as home, non-hospital institutions, etc., cannot be captured.

The above list of safety endpoints may be extended with additional sub-diagnoses or new health-related outcomes as agreed to by study researchers and Sponsor before the interim reports and final study report. These decisions will be made prior to initiation of analyses and documented in the SAP kept on file by the Sponsor.

In addition, the final study report will include the number of tofacitinib-exposed pregnancies.

9.4. Data Source

9.4.1. IBM Watson Health MarketScan® Research Databases

The data source for this analysis will be the IBM Watson Health MarketScan® claims database, a US administrative healthcare claims database. This database contains 143 million unique patients since 1996. Its sample size is large enough to allow for a nationally representative data sample of Americans with employer-provided health insurance, as well as Medicare and contains information on outpatient prescriptions and both inpatient and outpatient diagnoses. IBM Watson Health MarketScan® Research Databases include Commercial Claims and Encounters (Commercial) Database, Medicare Supplemental and Coordination of Benefits (Medicare Supplemental) Database, and the Lab Database. These databases represent healthcare claims information for individuals enrolled in various employer-sponsored healthcare plans. A subset of these individuals also receives benefits via Medicare supplemental insurance. The Commercial Database represents individuals covered under various commercial plans such as fee-for-service, capitated payment, preferred provider organizations, point-of-service, indemnity, and health maintenance organizations.

9.5. Study Size

This is a descriptive study and all eligible patients in Marketscan who have received ≥1 tofacitinib prescription from November 2012 (time of first US approval for tofacitinib) through to the end of data collection (30 June 2025) will be included, with no upper limit on the sample size. A preliminary analysis of the Marketscan database (using data from 2016

through to 2018) indicates that there are 11,857 patients who have received at least one prescription of tofacitinib, and59,080 patients who have at least 1 UC diagnosis from an inpatient visit or at least 2 UC diagnoses from outpatients visits, with at least one of these codes documented by a gastrointestinal specialist.

9.6. Data Management

Statistical analyses will be performed using SAS version 9.4 (Cary, NC). All analyses will be carried out under the direction of researchers at the University of Alabama, Birmingham (UAB) who will oversee all data analyses and provide direct biostatistical input. Statistical analysis will be completed only after all data have been entered, imported into and cleaned in SAS. To ensure the integrity and quality of the study results, UAB will follow standard operating procedures for programming validation for all analyses.

9.7. Data Analysis

Detailed methodology for summary and statistical analyses of data collected in this study will be documented in a statistical analysis plan (SAP), which will be dated, filed and maintained by the Sponsor. However, a brief overview of the analysis plan is provided in the subsections below. The SAP may modify the plans outlined in the protocol; any major modifications of endpoint definitions or their analyses would be reflected in a protocol amendment.

9.7.1. Assessment of tofacitinib utilization patterns

Categorical variables will be summarized using frequencies and proportions; continuous variables will summarized using means with standard deviations and/or medians with interquartile ranges, as appropriate. Age will be reported as a continuous variable and in clinically relevant categories, to identify off-label pediatric use (e.g. use in patients younger than 18 years prior to September 2020 and who do not have a pcJIA diagnosis) and use among elderly patients (i.e. 65 years or older).

The proportions of patients with an on-label, off-label, or unknown tofacitinib indication will be estimated with corresponding 95% confidence intervals (CIs). Patients who are prescribed tofacitinib for on-label, off-label and unknown indications will be described in terms of demographics (age, sex), comorbidities, prior and current medications (in terms of comedications not recommended for use while on tofacitinib i.e. biologic DMARDs, biologic therapies for UC or potent immunosuppressants such as azathioprine and cyclosporine as described in Table 2), as well as prescribed DD and duration of tofacitinib therapy. As it is expected that tofacitinib is more likely to be used off-label in non-approved rheumatic (e.g. psoriasis, ankylosing spondylitis) and IBD conditions (e.g. Crohn's disease), to identify off-label indications, diagnosis codes for other non-approved rheumatic and IBD conditions will be targeted. Among patients with on-label (approved) indications (i.e. RA, PsA, UC, pcJIA), tofacitinib dose will be assessed (as described in Section 9.3.2) and classified as on-label dose or off-label dose according to each prescription of tofacitinib. The proportion of tofacitinib prescriptions with off-label dosing, stratified by approved indication, will be estimated.

To further assess on-label/off-label use of tofacitinib, the proportion of TNFi-naïve UC patients prescribed tofacitinib prior to 01 July 2019 (on-label) and post 01 July 2019 (off-label) will also be estimated and described. Additionally, to further understand off-label dosing among patients with non-UC approved indications such as RA, PsA and pcJIA, the proportions of non-UC patients on 10 mg twice daily/22 mg once daily therapy will also be estimated and reported.

Among UC patients, the proportion of UC patients on 5 mg twice daily/11 mg once daily and 10 mg twice daily/22 mg once daily maintenance therapies, as well as the proportion of patients with approved indications (i.e. RA, PsA, UC, pcJIA) who have ≥1 thrombosis risk factors and are prescribed tofacitinib, overall and stratified by dose, will also be estimated and described.

Patients will be followed from the date of first tofacitinib prescription until death or end of data collection (whichever comes first) to estimate prescribed DD, and cumulative duration of use during the study period.

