7. RATIONALE AND BACKGROUND

Ulcerative colitis (UC) is a type of inflammatory bowel disease (IBD) characterized by chronic inflammation of the gastrointestinal tract, marked by an abnormal immune response. UC is restricted to the colon and affects the mucosa of the gut¹. As a result of the inflammatory reaction, the intestinal wall is damaged, frequently leading to bloody diarrhea and abdominal pain.

UC presents significant health and socioeconomic burdens for the individual patient and society^{6,7,8}. There is currently no cure for UC¹. Moderate-to-severe UC often requires treatment with systemic agents, such as glucocorticoids and azathioprine⁹, many of which are associated with infectious, cardiovascular, gastrointestinal and malignant adverse events^{10,11}. Tofacitinib, an inhibitor of the Janus kinase (JAK) family of kinases, was approved in the United States (US) in May 2018 at a dose of 5 mg twice daily or 10 mg twice daily for the treatment of adults with moderate-to-severe UC. In July 2019, the US prescribing information (USPI) was updated to note that tofacitinib should be prescribed for adult patients with moderate-to-severe UC who have had an inadequate response or who are intolerant to tumor necrosis factor inhibitors (TNFis). In December 2019, the extended-release formulation was also approved for UC patients at a dose of 11 mg once daily and 22 mg once daily. Use of tofacitinib in combination with biological therapies for UC or with potent immunosuppressants such as azathioprine and cyclosporine is not recommended.

Tofacitinib is also currently approved for three other indications in the US, and these include in adults with moderate-to-severe rheumatoid arthritis (RA) who have had an inadequate response or intolerance to methotrexate (MTX), in adults with active psoriatic arthritis who have had an inadequate response or intolerance to MTX or other disease-modifying antirheumatic drugs (DMARDs), and in patients ≥2 years with active polyarticular course

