9.2.1.1. Drug Utilization Study

To assess utilization patterns of tofacitinib use, all patients enrolled in the Marketscan database during the study observation period (i.e. from time of first US approval for tofacitinib in 2012 through to end of data collection in 2025) who have received ≥ 1 prescription of tofacitinib will be included.

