9.2.2. Exclusion Criteria

To assess to facitinib utilization patterns, no exclusion criteria will be applied. However, for the active surveillance population which will consist of a subset of the study population, patients not meeting the inclusion criteria for any of the respective cohorts described above will be excluded.

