- 3. After December 2017, a patient whose first tofacitinib prescription occurred after a diagnosis of PsA (defined as either as having ≥ 1 inpatient or ≥ 2 outpatient PsA diagnosis codes on two unique calendar days, with at least one from a rheumatologist), OR
- 4. Between May 2018 and July 2019, a patient whose first tofacitinib prescription occurred after a diagnosis of UC (defined as the first UC diagnosis code from an inpatient visit or after the second UC diagnosis code from an outpatient visit), OR
- 5. After July 2019, a patient whose first tofacitinib prescription occurred after a diagnosis of UC (as defined above) AND after evidence of prior TNFi use (i.e. using all available data, a prescription for ≥1 TNFi agent prior to first tofacitinib prescription), OR
- 6. After September 2020, a patient aged ≥2 years whose first tofacitinib prescription occurred after a diagnosis of pcJIA (defined as either as having ≥ 1 inpatient or ≥ 2 outpatient pcJIA diagnosis codes on two unique calendar days, with at least one from a rheumatologist)

In contrast, off-label indications will be defined as use of tofacitinib among patients with other diagnoses (i.e. lack of diagnosis codes for RA, PsA, UC or JIA) not fulfilling any of the conditions outlined above. If off-label use among non-approved indications occurs, it is expected that tofacitinib will be more likely used among patients with other non-approved rheumatic conditions (e.g. psoriasis, ankylosing spondylitis) or other non-approved IBD conditions (e.g. Crohn's disease). Thus off-label indications will be identified by broadly targeting diagnosis codes for other non-approved rheumatic and IBD conditions. Additionally, if the indications for which tofacitinib is prescribed cannot be determined from the available data, these will be classified as unknown indications and will evaluated separately as described in Section 9.7.1.

Among patients with on-label indications, to facitinib dose will be assessed. For each of these patients, every to facitinib prescription will be classified as on-label or off-label based on the labeled dose for the patient's indication at the time of prescription. Thus, for the

purposes of this analysis, on-label dose of tofacitinib will be defined, based on each tofacitinib prescription, using the following criteria:

- 1. Between November 2012 and November 2017, a prescription of tofacitinib 5 mg twice daily occurring only after a diagnosis of RA (as defined above)

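### The TNFi-naïve UC analysis calls all use before 01 July 2019 on-label but sets no start date, so it takes in UC use from before the 30 May 2018 approval

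*Protocol*

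**What the plan says.** Section 9.7.1 will report the "proportion of TNFi-naïve UC patients prescribed tofacitinib prior to 01 July 2019 (on-label) and post 01 July 2019 (off-label"). The data analysis paragraph of the abstract uses the same labels. The objective in Section 8 gives only the split at 01 July 2019, without the on-label and off-label tags.

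The population for this analysis is set in Section 9.2.1.1. It runs "from time of first US approval for tofacitinib in 2012 through to end of data collection in 2025". Section 9.2.2 adds that for the utilization part "no exclusion criteria will be applied".

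Three other places fix when UC use is on-label:

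- Table 2 dates the first UC approval 30 May 2018.
- Section 9.3.2, item 4, makes UC use on-label without a TNFi condition: "Between May 2018 and July 2019, a patient whose first tofacitinib prescription occurred after a diagnosis of UC". Item 5 then adds the TNFi condition: "After July 2019, a patient whose first tofacitinib prescription occurred after a diagnosis of UC (as defined above) AND after evidence of prior TNFi use".
- Section 9.3.6 gives the governing principle: the "classifications will be made based on the authorized indication(s) as of the index date".

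On the label change itself, Section 7 gives only the month: "In July 2019, the US prescribing information (USPI) was updated".

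**The concern.** The cut at 01 July 2019 exists because the US label changed in July 2019. The 'pre' group is useful as a baseline if it covers the time when a TNFi-naïve UC patient could receive tofacitinib on-label. With no lower bound, it also takes in UC patients first treated between November 2012 and 29 May 2018, when UC was not an approved indication.

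Two things follow. Those patients carry an on-label tag that the protocol's own definition denies them. Their TNFi history also enters the 'pre' proportion, and patients given a drug before approval in their disease may differ in prior treatment from those treated after it. This is a listed objective, so a reader of the final report would take the 'pre' figure as describing on-label prescribing.

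**Working it through.** **Step 1: apply the rules to one patient.** Take a TNFi-naïve adult with UC and no other approved indication, first prescribed tofacitinib between 06 November 2012 and 29 May 2018.

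| Rule | Result |
|---|---|
| 9.2.1.1 and 9.2.2 | In the utilization population |
| 9.3.2 items 2, 3, 6 (RA, PsA, pcJIA) | Not met |
| 9.3.2 item 4, with Table 2 (UC from 30 May 2018) | Not met, prescribed too early |
| 9.3.2 item 5 (UC with prior TNFi) | Not met |
| 9.3.6 (indication authorized at index date) | UC not authorized, so not on-label |
| 9.7.1 and abstract | On-label, because before 01 July 2019 |

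The last row contradicts the rows above it.

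**Step 2: calendar length.** Inputs are 06 November 2012 (RA approval, Table 2), 30 May 2018 (UC approval, Table 2) and 01 July 2019 (Section 9.7.1).

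- 06 November 2012 to 29 May 2018: 2,031 days
- 30 May 2018 to 30 June 2019: 397 days
- Total 'pre' period as written: 2,031 + 397 = 2,428 days
- Pre-approval share of time: 2,031 / 2,428 = 83.6%

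**Step 3: what this could mean in patients.** The protocol gives no count of UC users before approval, so this step rests on assumption. Let r be the daily rate of TNFi-naïve UC starts before approval, relative to the rate between 30 May 2018 and 30 June 2019. The share of the TNFi-naïve 'pre' group wrongly tagged on-label is

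share = 2,031r / (2,031r + 397)

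| r (assumed) | Share |
|---|---|
| 0 | 0% |
| 0.01 | 20.31 / 417.31 = 4.9% |
| 0.05 | 101.55 / 498.55 = 20.4% |
| 0.10 | 203.1 / 600.1 = 33.8% |
| 0.25 | 507.75 / 904.75 = 56.1% |

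**Step 4: effect on the proportion.** Read the proportion as TNFi-naïve patients among UC starters. Let f be the share of all 'pre' UC starters who began before approval, and let p1 and p0 be the naïve proportions after and before approval. The pooled value is (1 − f)p1 + f·p0, which differs from p1 by f(p0 − p1). With p1 = 30% and f from 10% to 30%, all assumed:

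- p0 = 5% to 15% gives 22.5% (0.7 × 30 + 0.3 × 5) to 28.5% (0.9 × 30 + 0.1 × 15)
- p0 = 60% gives 33% (0.9 × 30 + 0.1 × 60) to 39% (0.7 × 30 + 0.3 × 60)

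The error can go either way, and it vanishes if f = 0 or p0 = p1.

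**Step 5: the July 2019 boundary.** Section 9.7.1 cuts at a day. Section 9.3.2 names only the month. July 2019 has 31 days, which is 31 / 2,192 = 1.4% of the period from 01 July 2019 to 30 June 2025. As worded in 9.7.1, 01 July 2019 itself falls in neither group.

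**The case against.** The main classification is sound. Sections 9.3.2 and 9.3.6 start UC at its approval, and the disputed sentence is a supplement to that endpoint. Section 9.7 describes itself as an overview, and an analyst who applied 9.3.2 would probably notice the clash. This limits the damage but does not remove the contradiction. The label is stated outright in 9.7.1 and again in the abstract, and the same section does set a calendar bound where it needs one, for paediatric use before September 2020.

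Several stronger readings are tempting, and the protocol does not support them.

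- A reader might infer that 9.3.2 places the label change at the end of July 2019, so that a July starter is on-label there and off-label in 9.7.1. The text gives only a month. Elsewhere in 9.3.2 a rule worded as after a month stands for an approval within that month: November 2012 for RA (06 November in Table 2) and December 2017 for PsA (14 December). Taken literally, the dose rules would leave December 2017 RA prescriptions under no rule. What stands is month-level wording beside a day-level cut.
- A reader might blame the July boundary for part of the mixing in 'pre'. July 2019 starters cannot enter 'pre' under 9.7.1.
- A reader might take 83.6% as a share of patients. It is a share of days.
- A reader might say that every prescription is mislabelled. The text labels patients, and 9.3.6 classifies by first prescription.
- A reader might call the pre-approval UC patients off-label. Section 9.3.2 words off-label as "use of tofacitinib among patients with other diagnoses (i.e. lack of diagnosis codes for RA, PsA, UC or JIA"), which does not clearly fit a patient with UC codes. 'Not on-label' is the safer description.
- A reader might speak of a biased test of change. The two proportions are only described, and Section 9.1 specifies no hypotheses.

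**Conclusion.** The point holds for the missing lower bound. Section 9.7.1 and the abstract call TNFi-naïve UC use before 01 July 2019 on-label, while Table 2, Section 9.3.2 item 4 and Section 9.3.6 allow that only from 30 May 2018. Followed as written, the analysis counts pre-approval UC starters with no other approved indication as on-label and pools them into the 'pre' proportion. The size cannot be derived from the protocol. It depends on how many UC patients started before approval and on how their TNFi history differed, and it could be near zero. The percentages in steps 3 and 4 are illustrations under assumed inputs, not estimates. The main on-label/off-label endpoint is not affected. The July 2019 wording is a minor inconsistency. The correction is worth making because a listed objective is involved and the change is small.

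**What to change.** In Section 9.7.1 and in the data analysis paragraph of the abstract:

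- Define 'pre' as first tofacitinib prescription from 30 May 2018 to 30 June 2019.
- Define 'post' as first tofacitinib prescription from 01 July 2019, which also settles where that day falls.
- Report UC patients who started before 30 May 2018 on a separate line, as pre-approval (not on-label) use.

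As a minor point, use one day-level date for the label change in both 9.3.2 (items 4 and 5) and 9.7.1. Section 7 gives only the month, so the sponsor should confirm the day.

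The cost is a wording change and one extra table row. The 'pre' group becomes somewhat smaller and its confidence interval wider.

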9.2.1.2. Active surveillance study

The active surveillance population to be used for the estimation of the incidence rates of the safety events of interest will be a subset of the population described above, and will include all adult UC patients aged ≥18 years who are enrolled in the Marketscan database from the time of approval of tofacitinib for UC in the US (May 2018) through to the end of data collection (June 2025) for the study. UC patients will be identified via ICD-10 codes listed in Table 1. Using all available data, UC patients must have at least one UC diagnosis code from an inpatient visit, or at least two occurrences of a UC diagnosis code from outpatient vists, with at least one of the two outpatient codes documented by a gastrointestinal specialist. UC codes assigned on different dates do not need to be the same to qualify. At least 12 months of continuous (i.e., no more than a 30-day gap) database enrollment before index date is required to enable analysis of baseline patient and disease characteristics that may be important modifiers of the relationship of UC with safety endpoints of interest. Index date is defined in the treatment cohort inclusion criteria listed in the subsections below.

ICD-9 Code	Diagnosis	ICD-10 code	Diagnosis
556 (no 3 rd digit)	Ulcerative colitis		
556.0	Ulcerative enterocolitis	K51.8 (all billable codes under K51.8)	Other UC
556.1	Ulcerative ileocolitis	K51.8 (all billable codes under K51.8)	Other UC
556.2	Ulcerative proctitis	K51.2 (all billable codes under K51.2)	Ulcerative (Chronic) Proctitis
556.3	Ulcerative proctosigmoiditis	K51.3 (all billable codes under K51.3)	Ulcerative (Chronic) Rectosigmoiditis
556.5	Left-sided ulcerative colitis	K51.5 (all billable codes under K51.5)	Left Sided Colitis
556.6	556.6 Universal ulcerative colitis		Ulcerative (Chronic) Pancolitis
556.8	Other ulcerative colitis	K51.8 (all billable codes under K51.8)	Other Ulcerative Colitis
556.9	Ulcerative colitis, unspecified	K51.9 (all billable codes under K51.9)	Ulcerative Colitis, Unspecified

Table 1. ICD Codes for UC Diagnoses within MarketScan Database

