9.3.5. Follow-up in the active surveillance population

Patients in the active surveillance population will be followed from index date until first occurrence of each outcome of interest, treatment switch or discontinuation, with the appropriate outcome-specific extension to exposure (i.e. 90 day window for acute events, and "once-exposed always at risk" approach for non-acute events like malignancy as described below), and with death, lost medical/pharmacy coverage, and end of data collection (30 June 2025) treated as censoring events.

Acute events of interest in this study are thought to potentially occur at a higher rate while on drug, but that increased risk subsides after the drug is discontinued (i.e., serious and opportunistic infections, herpes zoster reactivation, MACE, VTE, GI perforation, PML). These events will be evaluated over a risk window that includes time from drug initiation until 90 days after end of treatment. When a patient initiates a new therapy within the 90-day

[figure not shown]
extension, the time and events during the overlapping period will be assigned to both treatments. An example of the as-treated approach with the 90-day extension period is provided in the scenario illustrated below.

------ represents risk period counted
+++++ represents time not included in the risk period
x represents occurrence of an acute safety event of interest such as MACE
) represents drug discontinuation
| represents tofacitinib initiation
| represents biologic initiation
| represents 90-day extension period

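### The utilization study does not end follow-up at loss of coverage and requires no prior enrolment, so time to discontinuation is understated and some UC patients are wrongly counted as TNFi-naive

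*Protocol*

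**What the plan says.** **End of follow-up.** Section 9.7.1 has utilization patients "followed from the date of first tofacitinib prescription until death or end of data collection (whichever comes first", and the purpose of this follow-up is "to estimate prescribed DD, and cumulative duration of use during the study period". For the safety cohorts, Section 9.3.5 ends follow-up "with death, lost medical/pharmacy coverage, and end of data collection (30 June 2025) treated as censoring events". On death, Section 9.3.6 notes that "only in-hospital deaths can be captured".

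**Entry.** Section 9.2.1.1 takes all enrolled patients "who have received ≥ 1 prescription of tofacitinib will be included", and Section 9.2.2 adds that for the utilization part "no exclusion criteria will be applied". For active surveillance, Section 9.2.1.2 sets a different rule: "At least 12 months of continuous (i.e., no more than a 30-day gap) database enrollment before index date is required".

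**Definitions that depend on these rules.** Section 9.3.3 measures duration from the first tofacitinib prescription to discontinuation and leaves the operational detail to the SAP. Section 9.7.1 summarizes continuous variables by means or medians. Under Section 9.3.2, prior TNFi use counts only if a TNFi claim is found in the patient's available data, and an indication that the data cannot show is classed as unknown. Section 9.7.1 labels TNFi-naive UC use on-label before 01 July 2019 and off-label after it.

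**The concern.** A claims database sees a patient only while the patient is insured. When coverage stops, fills stop, whether or not the patient is still taking the drug. When coverage starts, earlier fills and diagnoses are usually invisible. The surveillance part handles both limits, by censoring at loss of coverage and by requiring 12 months of enrolment before the index date. The utilization part handles neither.

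Two groups of Research Question 1 outputs are exposed. One is duration of therapy. The other is the set of proportions that depend on history before the first fill: the share with unknown indication, and the TNFi-naive share of UC users before and after 01 July 2019. The TNFi-naive share after that date is read as off-label use, in a study that serves an FDA commitment and the EU risk management plan. An upward error there would look like a prescribing finding when it is partly insurance turnover.

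**Working it through.** The protocol states no duration, turnover rate or TNFi-naive share, so there is no figure to reproduce. The counts in Section 9.5 (11,857 tofacitinib users and 59,080 UC patients) are database counts and do not bear on this point. The check compares the rules and then illustrates their effect under stated assumptions.

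**1. The rules side by side**

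| Rule | Utilization | Active surveillance |
|---|---|---|
| End of follow-up | Death or end of data (9.7.1) | Also loss of coverage, as censoring (9.3.5) |
| Prior enrolment | None (9.2.1.1, 9.2.2) | 12 months continuous (9.2.1.2) |
| Method for time-based quantity | Means or medians (9.7.1) | Time to first event with censoring (9.7.2) |

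Only in-hospital deaths are visible, so for most patients the 9.7.1 rule runs to 30 June 2025 whether or not they are still observable.

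**2. Duration (illustration)**

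Assume exponential persistence with true mean m years, so the rate is 1/m. Assume independent loss of coverage with yearly probability q, so μ = −ln(1−q). If loss of coverage is read as discontinuation, the apparent mean is 1/(1/m + μ). Leaving such patients out for want of a discontinuation date gives the same value: in this model the mean time among those who discontinue while covered is also 1/(1/m + μ).

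Example: m = 1 and q = 20% give μ = 0.223, and 1/(1 + 0.223) = 0.82 year.

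| True mean | q = 10% | q = 20% | q = 30% |
|---|---|---|---|
| 0.75 year | 0.70 (−7%) | 0.64 (−14%) | 0.59 (−21%) |
| 1 year | 0.90 (−10%) | 0.82 (−18%) | 0.74 (−26%) |
| 2 years | 1.65 (−17%) | 1.38 (−31%) | 1.17 (−42%) |

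Medians behave the same way. With a discontinuation hazard of 0.5 per year the median is ln 2/0.5 = 1.39 years. Adding a coverage-loss hazard of 0.1 or 0.3 gives ln 2/0.6 = 1.16 or ln 2/0.8 = 0.87 years, which is 17% or 38% shorter.

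A simulation with m = 1, q = 20% and a uniform end of data over 0 to 7 years estimated the mean as person-time divided by discontinuations. It gave 0.82 year with coverage loss counted as discontinuation and 1.00 year with coverage loss censored.

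**3. TNFi-naive share (illustration)**

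Let p be the true TNFi-naive share among UC users with diagnosis codes. Let s be the share of TNFi-experienced users whose TNFi claims all predate enrolment. The apparent share is p + (1−p)s.

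Example: p = 20% and s = 10% give 0.20 + 0.80 × 0.10 = 28%. Of those called naive, 0.08/0.28 = 29% are misclassified.

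| True share | s = 5% | s = 10% | s = 20% | s = 30% |
|---|---|---|---|---|
| 10% | 14.5% | 19% | 28% | 37% |
| 20% | 24% | 28% | 36% | 44% |
| 30% | 33.5% | 37% | 44% | 51% |

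All of m, q, p and s are assumptions. The directions follow from the rules: duration is too short and the TNFi-naive share is too high.

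**The case against.** The strongest reply is that this belongs to the SAP. Section 9.3.3 defers the operational definition of duration, Section 9.7 calls itself an overview that the SAP may modify, and no sentence says that loss of coverage counts as discontinuation. This stands in part: the SAP could add the rule, and the percentages presuppose its absence. But the two end points of follow-up and the open entry are stated protocol rules, and they differ from the protocol's own rules for the same data. Section 9.9 speaks of exposure misclassification and of conclusions limited to the treatment captured. It names neither loss of coverage nor short look-back.

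Taking all users without exclusions is a sound choice for a count of users, and that also stands. The overall tables should remain.

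A reader might infer more than the documents support:

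- **Prescribed daily dose is biased.** Not shown. Section 9.3.3 computes it from days' supply and amount dispensed, so months without coverage need not enter it.
- **The Week 17 maintenance dose is biased.** Not shown. A patient who lost coverage earlier has no recorded dose and is missing, not misclassified. A patient already on drug at enrolment is past Week 17 in any case.
- **Cumulative use would change with a censoring date.** If it is summed from dispensed supply, it would not. The repair concerns time to discontinuation.
- **Any user with no history is counted as TNFi-naive.** No. Without UC codes before the first fill, a patient does not meet the UC definition and falls under unknown, the category made for such cases. Only UC patients with diagnosis codes and unseen TNFi claims are misclassified.
- **Twelve months of enrolment solves it.** It reduces the misclassification but does not remove it, since TNFi use can be older.

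**Conclusion.** The point holds for two outputs. Applied as written, Section 9.7.1 understates time from first prescription to discontinuation, because patients who leave coverage on treatment look as if they stopped. The open entry rule inflates the TNFi-naive share of UC users, hence apparent off-label use after 01 July 2019, and places some users under unknown only because their look-back is short.

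The size cannot be derived from the protocol. Over the assumed ranges, mean duration is 7% to 42% too short, and a true TNFi-naive share of 20% appears as 24% to 44%. These figures show sensitivity and are not estimates for this database. They rest on exponential persistence, independent coverage loss, and loss of coverage not being separated from discontinuation.

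The indication endpoint is fixed at the first prescription, so the follow-up rule does not affect it, although short look-back does. The primary malignancy rate is unaffected, because the surveillance part already has both safeguards.

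**What to change.** 1. In Section 9.7.1, add loss of medical or pharmacy coverage as an end of follow-up. Treat it and end of data as censoring, and report time to discontinuation by Kaplan-Meier.
2. Keep the all-user tables. Repeat the indication proportions and the TNFi-naive proportions before and after 01 July 2019 in users with at least 12 months of continuous prior enrolment, as defined in Section 9.2.1.2. Continue to search all data held on each patient for TNFi history.
3. State in Section 9.9 that TNFi use before enrolment remains unobserved, so the TNFi-naive share may still be too high in the restricted table.

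The cost is a few sentences and one repeated set of tables from data already held. The restricted tables will have fewer patients and wider confidence intervals, and showing both versions lets readers see how far the shares depend on look-back.
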